6.1 Study Assessments

6.1.1 Efficacy Assessments

Primary Endpoint: The response rate of R+P will be evaluated using RECIST 1.1 as well as iRECIST. Disease status will be measured by CT scan at baseline and then once every two cycles and as clinically indicated. Radiographic response per RECIST v.1.1 and iRECIST criteria (Appendices 1 and 2) will be determined by comparison to the tumor measurement obtained at baseline. Tumor progression will be determined by comparison to the smallest tumor measurement at either baseline or after initiation of therapy. The baseline disease assessment must be recorded and measured within 28 days prior to treatment start. During the treatment period, disease assessments will be performed every 6 weeks, i.e. once every two cycles, and as clinically indicated.

Secondary Endpoints: Safety and tolerability will be assessed with adverse event (AE) assessments at each study visit. CTCAE v5.0 will be used for adverse event grading. Attributions of causality will be assessed by the primary treating physician. Clinical benefit rate (stable disease + responses) will be assessed using the same criteria as response rate and on the same schedule. Survival will be measured from the date of study registration to the date of event (i.e., death or progressive disease) or the date of last follow-up if no event has occurred at their last evaluation.

6.1.2 Laboratory Assessments

Safety blood samples include complete blood count, clinical chemistry, including liver function test, and coagulation.

IRB Protocol Number: 2019C0145
IRB Approval date: 06/10/2022
Version: 05/06/2022

PROTOCOL NUMBER: OSU-19132

Blood (2 tubes x 10 ML): BD Vacutainer (heparin tubes) will be used for blood collection. Peripheral blood will be analyzed for circulating immune cell profiles in relation to clinical response using CyTOF profile at baseline and prior to cycle 3. Peripheral blood analysis will also include TCR immunosequencing (immunoSEQ) and VEGF (ELISA) at baseline, during treatment and at progression.

Peripheral blood for CyTOF profile will be collected at 3 time points (baseline and cycle 2, day 1 at progression/end of treatment) for the initial 13 patients (stage 1). If a patient discontinues treatment after cycle 2, EOT samples will be collected at that time. Peripheral blood mononuclear cells (PBMC) and plasma for remaining correlative studies (TCR immunoSEQ and VEGF) will be preserved from collected blood samples at 3 time points: baseline (pre-treatment day 1), prior to cycle 3, and at study discontinuation or disease progression. Correlative studies will be collected as scheduled even if one of the two drugs is held/discontinued.

Samples will be stored for batching of correlative studies (TCR immunoSEQ and VEGF).

IRB Protocol Number: 2019C0145
IRB Approval date: 06/10/2022
Version: 05/06/2022

PROTOCOL NUMBER: OSU-19132

6.2 Data Safety and Monitoring Plan

The data and safety monitoring plan will involve the continuous evaluation of safety, data quality and data timeliness. Investigators will conduct continuous review of data and patient safety at their regular disease group meetings (at least monthly) and the discussion will be documented in the minutes. The PI of the trial will review toxicities and responses of the trial where applicable at these disease group meetings and determine if the risk/benefit ratio of the trial changes. Frequency and severity of adverse events will be reviewed by the PI and compared to what is known about the agent/device from other sources; including published literature, scientific meetings and discussions with the investigators, to determine if the trial should be terminated before completion. Serious adverse events and responses will also be reviewed by the OSUCCC Data and Safety Monitoring Committee (DSMC). The PI will also submit a progress report (biannually for Phase II and quarterly for Phase I) that will be reviewed by the committee per the DSMC plan. All reportable Serious Adverse Events (SAE) will also be reported to the IRB of record as per the policies of the IRB.

Throughout the treatment period until one month after the last dose of study medication, patients will be assessed for all adverse events. National Cancer Institute Common Terminology Criteria for Adverse Events (CTCAE v 5.0) will be used for grading. If necessary, the patient may be withdrawn from the study treatment.

6.3 Schedule of Study Events

The Schedule of Study Events is shown in Table 4**Table 4**.

PROTOCOL NUMBER: OSU-19132

Table 4. Schedule of Study Events

Assessments	Screening/ Baseline			Cycle 1*	Cycle 1	Cycle 2	Cycle 2	Cycle 3 +	End of Treatment
Visit window [days]	Within 28 days	Within 10 days	Within 7 days	Day 1	Day 8	Day 1	Day 8	Day 1	30 days
						+/- 3 days		+/- 3 days	± 14 days
Informed consent ¹	X								
Inclusion and exclusion criteria		X							
Demographics		X							
Medical History ²		X							X
Pregnancy test (if applicable) ³		X						X	
Vital signs and weight ⁵		X		X	X	X	X	X	X
Physical examination and ECOG			X	X	X	X	X	X	X
Urine analysis ⁶		X		X	X	X	X	X	X
Hematology ⁷		X		X				X	X
Coagulation studies ⁸		X						X ⁷	
Complete Serum chemistry ⁹		X		X	X	X	X	X	X
TSH ¹⁰		X						X ⁹	
Peripheral blood correlative studies ¹¹				X				X ¹¹	X
Tumor biopsy ¹¹	X								X
Assessment of disease status ¹²	X							X	X
Ramucirumab dosing				X		X		X	
Pembrolizumab dosing				X		X		X	
Adverse event assessment				X		X		X	X
Concomitant Medication		X		X		X		X	X

Study Assessment Footnotes

PROTOCOL NUMBER: OSU-19132

* Each treatment cycle is 21 days

¹ Prior to the first study-specific assessments

² Medical history includes baseline symptoms as well as a detailed history of prior cancer therapies including start and stop dates, disease progression during or after therapy, as well as discontinuations due to intolerance or any other serious illness.

³ Applicable for women of childbearing potential. Serum β -HCG test within 14 days before the first dose of study drug.

⁴ Urine pregnancy test on day 1 of cycle 1 to confirm pregnancy status prior to treatment. Repeat urine pregnancy testing for women of childbearing potential every 9 weeks or if pregnancy is suspected. Positive urine pregnancy testing will require confirmation with serum pregnancy testing.

⁵ Vital signs: Weight, blood pressure, pulse and temperature

⁶ Urine analysis will include appearance, color, glucose, hemoglobin, ketones, pH, and protein. Microscopy will only be performed if clinically indicated. Urine dipstick protein $> 1+$ will require 24 hour urine collection for urine protein assessment. 24 urine collection will include measurement of both protein and creatinine.

⁷ Hematology: Complete blood count including differential is required. WBC differential may be automated or manual as per institutional standards.

⁸ Coagulation studies will include PT/INR and PTT. These studies will be repeated every 3rd cycle or as needed (for patients on active anti-coagulation).

⁹ Complete Serum Chemistry includes: sodium, potassium, chloride, bicarbonate, BUN, creatinine, glucose, calcium, phosphate, magnesium, ALT, AST, alkaline phosphatase, total bilirubin, total protein, albumin.

¹⁰ TSH will be performed at baseline - free T3/free T4 to be checked if TSH is out of the normal range.

¹¹ Correlative studies (peripheral blood) will be drawn pre-treatment on cycle 1 day 1; cycle 3 day 1, and at final study visit. Tumor biopsy sample (archival) will be collected at study enrollment. Optional tumor biopsy at progression if clinically indicated.

¹² Disease status will be measured by CT scan every 6 weeks (+/- 7 days) for the first 6 months and then every 12 weeks and as clinically indicated. Baseline imaging within 28 days of study initiation.

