	
Tumor type: EGFR mutation positive NSCLC
 
The proposed study will be an open-label single arm phase II trial of ramucirumab and pembrolizumab (R+P) in EGFR mutant NSCLC after progression on tyrosine kinase inhibitors (TKIs). Patients are required to receive at least one TKI (erlotinib, gefitinib, afatinib or osimertinib). Post-TKI chemotherapy is also permitted.
 
Each treatment cycle will be 21 days; patients will receive ramucirumab 10 mg/kg IV and pembrolizumab 200 mg IV and on day 1. Dosing of ramucirumab and pembrolizumab is based on prior phase 1 testing of the combination. A two-stage design will be utilized to minimize exposure to combination therapy if there is limited efficacy. The initial stage will enroll 13 patients; if ≥ 1 patient has a confirmed response, the study will continue and enroll an additional 21 patients for a total of 34 patients.
 
Response will be assessed using RECIST (RECIST 1.1 and iRECIST). Imaging will be performed every 6 weeks/2 cycles to assess response. Patients with clinical benefit may continue therapy beyond progression for up to 2 cycles – if progressive disease confirmed on repeat imaging, therapy would be discontinued. Toxicity will be assessed using CTCAE v5.0. Progression free survival will be assessed using RECIST and will be assessed starting from date of study enrollment.
 
Blood samples tissue will be collected at baseline (day 1, cycle 1), cycle 3 day1 (approx. 6 weeks), and at study discontinuation (or progression). Archival tissue will be requested at enrollment for correlative studies.

Duration of Treatment	Patients may continue to receive study treatment (R+P) until radiographic documentation of disease progression, the occurrence of unacceptable toxicity or of the occurrence of other withdrawal criteria. If either drug is discontinued due to toxicity, the other drug may be continued.
Inclusion /Exclusion Criteria	
Inclusion Criteria:
 
1. Adult patients aged ≥ 18 years

IRB Protocol Number: 2019C0145
IRB Approval date: 06/10/2022
Version: 05/06/2022

PROTOCOL NUMBER: OSU-19132

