2.3 Exploratory objectives

To characterize predictive immunologic biomarkers of response in tissue and peripheral blood of patients receiving ramucirumab and pembrolizumab combination therapy

Exploratory Endpoints: 1) Baseline tumor immunoprofile by IHC, including tumor infiltrating lymphocytes and T cell receptor (TCR) immunosequencing (immunoSEQ) and relationship to clinical outcomes, including response rate. 2) Circulating immune cell profiles in response to treatment and in relation to clinical response using CyTOF profile on peripheral blood samples. 3) Circulating VEGF at baseline, after treatment and at progression to evaluate correlation with clinical response

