3. INVESTIGATIONAL PLAN

3.1 Overview of Study Design and Dosing Regimen

The clinical trial will be an open-label, two-stage, single arm phase II trial of ramucirumab and pembrolizumab in EGFR mutant NSCLC after progression on at least one EGFR TKI.

Each treatment cycle will be 21 days. Patients will receive ramucirumab 10 mg/kg and pembrolizumab 200 mg IV on day 1. Dosing of pembrolizumab and ramucirumab is based on prior phase 1 testing of the combination.

All trial treatments will be administered on an outpatient basis.

The treatment to be used in this trial is outlined below in Table 2

Table 2: Trial Treatment

Drug	Dose/ Potency	Dose Frequen- cy	Route of Administration	Regimen/ Treatment Period	Use
Ramucirumab	10 mg/kg	Q3W	IV infusion	Day 1 of each 3 week cycle	Experimental
Pembrolizumab	200 mg	Q3W	IV infusion	Day 1 of each 3 week cycle	Experimental

Tumor tissue will be collected at baseline. Peripheral blood samples will be collected at baseline, cycle 3 day 1, and at progression (or study discontinuation).

During the treatment period, patients will undergo physical examination monthly and CT scans at baseline and then approximately every 6 weeks (2 cycles) thereafter. The disease status will be assessed per RECIST v.1.1 and iRECIST (immune RECIST) criteria (Appendices 1 and 2).

IRB Protocol Number: 2019C0145
IRB Approval date: 06/10/2022
Version: 05/06/2022

PROTOCOL NUMBER: OSU-19132

Patients will be treated for up to 35 cycles or until confirmed progression of disease or the development of unacceptable toxicities. All patients will then undergo a final visit (end of treatment visit).

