3.1.4 End of Treatment Visit

Patients that discontinue from treatment will undergo an end of treatment visit, regardless of the reason of discontinuation, 30 (+/- 14) days after the last dose of study medication.

This study to be conducted at The Ohio State University Wexner Medical Center. If the protocol meets criteria to proceed with enrollment after initial futility analysis, we will consider expansion to include additional sites.

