Medications or vaccinations specifically prohibited in the exclusion criteria are not allowed during the ongoing study. If there is a clinical indication for any medication or vaccination specifically prohibited during the study, discontinuation from study therapy or vaccination may be required. The final decision on any supportive therapy or vaccination rests with the investigator and/or the participant's primary physician. However, the decision to continue the participant on study treatment requires the mutual agreement of the investigator, the Sponsor and the participant.

There are no prohibited therapies during the Post-Treatment Follow-up Phase.

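### The third correlative blood draw is timed inconsistently (end-of-treatment visit versus progression or discontinuation), and nothing requires it to precede new anticancer therapy

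*Combined protocol and SAP*

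**What the plan says.** **The purpose of the sample.** Section 2.3 lists as an exploratory endpoint "Circulating VEGF at baseline, after treatment and at progression to evaluate correlation with clinical response". Section 9.1.3 names only baseline and after treatment for VEGF. Section 9.5 plans a plot of response against the peak VEGF value over time.

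**Timing in the schedule.** Table 4 (Section 6.3) marks the last peripheral-blood correlative draw in the End of Treatment column. Footnote 11 places the draws on cycle 1 day 1, "cycle 3 day 1, and at final study visit". Section 3.1 equates the final visit with the EOT visit: "All patients will then undergo a final visit (end of treatment visit". Section 3.1.4 sets that visit at "30 (+/- 14) days after the last dose of study medication", and Section 6.3.6 gives the same window.

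**Timing elsewhere.**
- Synopsis, Study Design: the last draw is "and at study discontinuation (or progression").
- Section 3.1: "Peripheral blood samples will be collected at baseline, cycle 3 day 1, and at progression (or study discontinuation").
- Section 6.1.3, specimen table: the third CyTOF, TCR and VEGF tubes stand under a heading that offers either end of treatment or progressive disease.
- Section 6.1.3, text for TCR and VEGF: "prior to cycle 3, and at study discontinuation or disease progression".
- Section 6.1.3, CyTOF text: for a patient who stops after cycle 2, the EOT samples are to be taken at the moment of stopping.

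**New therapy.** Section 8.4 bars other antineoplastic treatment during the Screening and Treatment Phase, then states: "There are no prohibited therapies during the Post-Treatment Follow-up Phase". Sections 1.4 and 7.2 end adverse-event recording at 30 days after the last dose or at the start of another anticancer therapy, whichever is earlier.

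**The concern.** The plan gives one tube two different dates. A site working from Table 4 draws at the EOT visit. A site working from Section 3.1 draws when progression or discontinuation occurs. Both comply, and the two samples would carry the same label.

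The difference matters most when a new regimen begins between stopping and the EOT visit. Sections 1.4 and 7.2 foresee that this can happen within 30 days, and no sampling rule guards against it. A VEGF or immune-cell value taken after a switch reflects the next treatment as well as the state at progression. It cannot be retaken. Such a value could also supply the peak in the Section 9.5 plot.

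The plan also does not separate third samples taken because of progression from those of patients who stop for toxicity or after 35 cycles. Section 3.1.4 contemplates adding sites after the first stage, which makes a single rule more useful.

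**Working it through.** The plan states no figure for the interval between progression and the third draw, so there is none to reproduce. The check is date arithmetic.

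**Inputs.** EOT visit at last dose + 30 ± 14 days (Sections 3.1.4 and 6.3.6, Table 4). Cycle of 21 days with dosing on day 1 (Section 3.1.1). First scan at 42 ± 7 days (Section 6.3.5). Up to 2 further cycles after first progression (synopsis, Section 1.5.3). Repeat imaging 4 to 8 weeks after first progression (Table 1).

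**Assumptions.** First dose on study day 1, so nominal doses fall on days 1, 22, 43 and 64. The progression scan is on day 42.

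**EOT window.** 30 − 14 = 16 and 30 + 14 = 44, so 16 to 44 days after the last dose.

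**Patient A: stopped at the day-42 scan, last dose on day 22.**
- The window alone gives 22 + 16 = day 38 to 22 + 44 = day 66.
- The EOT visit follows discontinuation, so it cannot precede the scan that caused the stop. The usable range is day 42 to day 66.
- Interval after the scan: 42 − 42 = 0 to 66 − 42 = 24 days.
- Letting the scan vary within ±7 days and counting elapsed days from the first dose (cycle 2 at 21 days), the scan falls 35 − 21 = 14 to 49 − 21 = 28 days after the last dose. The upper interval becomes 44 − 14 = 30 days. With the ±3-day dosing window it is 44 − 11 = 33 days. The choice of counting convention moves these figures by one day.

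**Patient B: progression on day 42, treated on days 43 and 64, then stopped.**
- EOT visit: 64 + 16 = day 80 to 64 + 44 = day 108.
- Interval after first RECIST 1.1 progression: 80 − 42 = 38 to 108 − 42 = 66 days.
- Order of events: repeat imaging is allowed from 42 + 28 = day 70, so a stop before day 80 is possible and the lower bound stands.

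**Is the draw protected from a new therapy?** Section 8.4 restricts therapy only during screening and treatment. Section 6.5 says that treatment after EOT is at the investigator's discretion, which is descriptive and sets no sampling rule. Section 6.3.6 ends follow-up imaging at the start of a new anticancer treatment, but no comparable limit exists for the blood draw. Nothing found orders the draw before a switch.

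**Do the other sections resolve the conflict?** The synopsis, Section 3.1 and the TCR/VEGF text of Section 6.1.3 tie the draw to the event. The specimen table accepts either time, so an EOT draw satisfies it even if no sample was taken at progression. The CyTOF text fixes the time of stopping for patients who stop after cycle 2, which for them contradicts Table 4. No section says which text prevails.

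**The case against.** The strongest case on the other side has five parts.

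- **Footnote 11 is not the only schedule.** Several sections call for or allow a draw at the event, and Section 6.1.3 directly addresses the patient who stops after cycle 2. This stands. A reader might infer from Table 4 that the sample does not measure progression on study drug; the documents do not establish that. What they show is a conflict.
- **Time off drug is largely inherent.** A day-42 scan is itself 42 − 22 = 20 days after the last nominal dose, inside the 16-to-44-day window. This stands, so washout alone is not the problem.
- **Frequency is unknown.** A reader might infer that many third samples will be drawn on another regimen, or that this will vary with outcome. No section gives a rate. Section 6.5 describes further treatment as following EOT, and no section places the EOT visit in the phase to which the unrestricted-therapy sentence of Section 8.4 applies. Only the possibility is documented.
- **The analysis is modest.** Section 9.5 plans no formal comparison at progression and no resistance analysis. It calls the work descriptive and exploratory. This stands and limits the consequence.
- **Moving the draw to first RECIST 1.1 progression could do harm.** A reader might think that the natural repair. Under Appendix 2, first progression may prove to be pseudo-progression and be reset, and the only third sample would then describe a flare. This stands, and it is why the draw is better tied to stopping treatment.

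What survives is the inconsistency, the missing rule on new therapy, and the lack of any distinction between progression and other EOT samples.

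**Conclusion.** The point holds as an unreconciled timing conflict with a missing safeguard. Under nominal dosing and a day-42 progression, a Table 4 draw falls 0 to 24 days after the scan for a patient stopped there, and 38 to 66 days after first progression for a patient treated two more cycles. It may follow a change of therapy.

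The number of patients affected cannot be estimated from the documents. The ceiling for VEGF and TCR is one third sample per patient, at most 34; Section 6.1.3 describes the three-point CyTOF collection for the first 13 patients only.

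The effect is confined to descriptive exploratory endpoints, chiefly VEGF at progression and the peak-VEGF plot. Response rate, safety, PFS and OS are untouched. The change is worth making because it is cheap and a mistimed sample cannot be recovered.

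**What to change.** Amend Table 4 and footnote 11 to agree with the synopsis, Section 3.1 and Section 6.1.3:

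1. Take the third draw when study treatment is stopped, for progression or any other reason, and before any new anticancer therapy. Use the EOT visit as a fallback only if no new therapy has begun. This governs the tube, not the patient's care.
2. Record the reason for the draw and its date relative to last dose, first progression, confirmed progression and the start of new therapy.
3. State in Section 9.5 that progression samples are summarised separately from other EOT samples, and that post-switch samples are left out of the progression and peak-VEGF summaries.

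The cost is wording and a few date fields, with the same number of tubes. A few samples will be excluded when the draw is missed before a switch. For a patient treated past first progression, the draw will still come weeks after that first scan: 28 to 56 days if treatment stops at repeat imaging 4 to 8 weeks later (4 × 7 and 8 × 7). That is why both progression dates should be recorded.

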6.3.1 Screening Assessments

All patients will be screened and screening procedures performed within 10 days (unless otherwise noted) prior to the start of induction treatment. These include the following:

Signed written informed consent	Obtained prior to any study specific assessments
Inclusion/Exclusion Criteria (Day -28 to 1)	
 • Age • Tumor diagnosis • Prior therapies • Comorbid conditions
Demographics and Medical History	
 • Age, gender, ethnic background • Previous and concurrent relevant diseases • Current symptoms and/ or residual toxicities from prior therapies • Details on prior cancer therapy, including start and stop dates, disease progression during or after therapy, as well as discontinuation due to toxicities
Concomitant medication	Concomitant medication currently used will be documented.
Pregnancy test (if applicable)	A serum pregnancy test will be performed in women of child-bearing potential: pre-menopausal women and women who are post-menopausal for < 2 years.
Physical examination and vital signs (Day -7 to 1)	
 • Body height and weight • Vital signs: Blood pressure, pulse, temperature • Physical examination • ECOG performance status (Appendix 3)
Urine analysis	Appearance, color, urine bilirubin, glucose, hemoglobin, ketones, pH, protein, specific gravity, urobilinogen.
Hematology (CBC)	Hemoglobin, hematocrit, mean corpuscular volume, mean corpuscular hemoglobin, mean corpuscular hemoglobin concentration, white blood cell (WBC) count, WBC differential, red blood cell count, lymphocytes, monocytes, neutrophils, band neutrophils, eosinophils, basophils, platelets. WBC differential may be automated or manual as per institutional standards.

Complete Serum Chemistry	Sodium, potassium, chloride, bicarbonate, BUN, creatinine, glucose, calcium, phosphate, magnesium, ALT, AST, alkaline phosphatase, total bilirubin, total protein, albumin
Assessment of disease status (Day - 28 to 1)	The disease status will be measured by CT scan (Chest/Abdomen/Pelvis). MRI brain will be done as clinically indicated.
Tumor biopsy - archival	Archival tumor biopsy material (paraffin embedded and formalin fixed) will be collected, if available. If standard of care biopsy is performed, fresh tumor cells will be collected for study.

